### **8.3 Adverse Events Definitions and Reporting Requirements**

#### **8.3.1 Adverse Events**

An AE is defined as any untoward medical occurrence in a clinical research participant administered an investigational product and which does not necessarily have a causal relationship with the investigational product. As such, an AE can be an unfavorable or unintended sign (including an abnormal laboratory finding, for example), symptom or disease temporally associated with the use of an investigational product, whether or not considered related to the product. This definition is applied to all groups beginning at the time of enrollment (i.e., once a participant is randomized) through to the termination visit. The term “investigational product” for this study refers to the placebo rectal insert, the placebo (water) rectal douche, and the placebo rectal suppository.

Study participants will be provided instructions for contacting the study site to report any untoward medical occurrences they may experience. In cases of potentially life-threatening events, participants will be instructed to seek immediate emergency care. Where feasible and medically appropriate, participants will be encouraged to seek evaluation where a study clinician is based, and to request that the clinician be contacted upon their arrival. Records from all non-study medical providers related to untoward medical occurrences will be obtained whenever possible and with appropriate permission of the participant, and required data elements will be captured in the study database. All participants reporting an untoward medical occurrence considered related to product use will be followed clinically until the occurrence resolves (returns to baseline) or stabilizes.

Study site staff will document in source documents and in the study database all AEs reported by or observed in enrolled study participants regardless of severity and presumed relationship to study product. AE severity will be graded per the DAIDS Table for Grading Adult and Pediatric Adverse Events, Corrected Version 2.1, July 2017 and/or Addenda 1, 2 and 3 (Female Genital [Dated November 2007], Male Genital [Dated November 2007] and Rectal [Clarification Dated May 2012] Grading Tables for Use in Microbicide Studies), available on the DAIDS Regulatory Support Center (RSC) website at <http://rsc.tech-res.com/clinical-research-sites/safety-reporting/daids-grading-tables>.

For individuals with a vagina or neovagina, please note:

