#### Rectal products

Side effects observed with application of rectal products in previous research studies include: mild rectal fullness; incontinence or diarrhea; flatulence; mild abdominal pain; anal discharge and proctalgia.

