2.5 Sample Size and Power

There is no control group for comparison in this study. The goal is not to compare each product to some standard but instead to estimate overall rates of acceptability, adherence and safety.

Primary Endpoints – Acceptability/Tolerability and Adherence

Based on previous studies we expect to observe a high rate of acceptability (>80%) which equates to $\leq 20\%$ of participants reporting a low likelihood of using the product in the future (≤ 3 on the rating scale). Likewise, we expect to observe a high rate of participants reporting taking at least 90% of expected doses.

The table below shows the exact confidence intervals for acceptability and adherence, assuming $\alpha=0.05$ based on the Binomial distribution and varying rates of acceptability and adherence. The power to rule out <50% and <70% acceptability or adherence given the rates is also shown. Calculations assume the outcomes are observed in 200 of the participants (5% loss to follow-up). For example, if the true acceptability or adherence rate is 90%, we have 100% power to rule out a true acceptability or adherence rate of 75% or lower. If we observe an 80% acceptability or adherence rate, the corresponding 95% confidence interval (CI) will be (74%, 85%).

Table 2: Exact 2-sided 95% Confidence Intervals Based on Various Rates of Acceptability or Adherence Endpoints

Acceptability rate / adherence rate	95% CI if rate is observed	Power to rule out 50% if rate is true	Power to rule out 70% if rate is true	Power to rule out 75% if rate is true
95%	(91, 98)	100%	100%	100%
90%	(85, 94)	100%	100%	100%
85%	(79, 90)	100%	100%	93%
80%	(74, 85)	100%	90%	35%

Primary Endpoint – Safety

To characterize the statistical properties of the safety endpoint, the table below presents the probability of observing zero, at least one, and two or more safety endpoints among 200 participants (allowing for the possibility of 5% dropout) assuming various “true” event rates. By assuming that we may only have safety evaluations on 200 participants, these calculations are conservative. However, safety analyses will include all enrolled participants.

Table 3: Analysis of Safety Event Frequency

Event Rate	P(0 events n=200)	P(≥ 1 event n=200)	P(≥ 5 events n=200)	P(≥ 10 events n=200)
0.1%	82%	18%	0%	0%
0.5%	37%	63%	0%	0%
1%	13%	87%	5%	0%
2%	2%	98%	37%	1%
5%	0%	100%	97%	55%

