9.1 Primary Safety Analyses

The primary safety endpoint is defined as follows:

Grade 2 or higher related adverse events (AEs) as defined by the Division of AIDS Table for Grading the Severity of Adult and Pediatric Adverse Events, Corrected Version 2.1, July 2017, and/or Addenda 1, 2 and 3 (Female Genital [Dated November 2007], Male Genital [Dated November 2007] and Rectal [Clarification Dated May 2012] Grading Tables for Use in Microbicide Studies)

The number and the percentage of participants experiencing each safety endpoint will be tabulated by study product. This table will display a summary for any primary safety endpoint and for each individual safety endpoint. Each participant will contribute once in each category (i.e., only for highest severity AE for each participant) for the calculation of event rates for each study product. Exact binomial confidence intervals (Clopper-Pearson) will be calculated for each safety endpoint, even if no events occur for an endpoint for a particular study product.

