9.3 Other Safety Measures

Additional safety summaries include:

The number and percentage of participants with a positive result for hCG for pregnancy and HIV will be displayed in a table overall and by site if applicable. A listing of participants with positive results of STI testing (syphilis, trichomonas, gonorrhea, chlamydia) after first study product use will be presented if applicable.

A listing of participants with abnormal findings on rectal exam after first study product used will be presented.

A listing of all concomitant medications will be presented.

10. Exploratory Analysis

In addition to the analyses described above, the following analyses will be conducted to compare and estimate the relative acceptability/tolerance, adherence and safety between the three study products. These analyses will also allow to assess potential effects of the order of product use on each of the endpoints.

A logistic mixed effects regression model will be used to estimate the relative odds (odds ratios) of high acceptability between the different study products. A similar logistic mixed effects regression model will be used to estimate the relative odds (odds ratio) of full per-protocol and per-sex-act adherence between the different study products. To account for the cross-over design of the study, a random intercept at the participant level will be included in the models. Estimates of the odds-ratios, along with 95% confidence intervals and associated p-values will be reported. If feasible, testing for effects of the order of product use will be done by including interaction terms between study product and randomized sequence in the model.

A logistic mixed effects regression model will be used to estimate the relative odds (odds ratio) of having a primary safety endpoint, as defined in section 9.1, between the different study products. A Poisson mixed effects regression model will be used to compare the incidence (expected counts) of AEs per study period between the study products. If feasible, interaction terms between study product and randomized sequence will be included in the model to test the effect of order of product use on the safety endpoints.

11. References

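### SAP section 10's exploratory Poisson model for AE counts states no allowance for AEs that cluster within a participant-period; if they do cluster, its intervals and p-values are too narrow

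*SAP*

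**What the plan says.** SAP section 10 (Exploratory Analysis) has two modelling paragraphs.

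- The first covers acceptability and adherence with logistic mixed models. It says "a random intercept at the participant level will be included in the models", and then "Estimates of the odds-ratios, along with 95% confidence intervals and associated p-values will be reported".
- The second covers safety. After a logistic mixed model for the primary safety endpoint, it states: "A Poisson mixed effects regression model will be used to compare the incidence (expected counts) of AEs per study period between the study products". It gives no random-effect structure of its own beyond the word mixed. It mentions no dispersion parameter, negative binomial model, period-level random effect or robust variance. It does not say whether all AEs or only Grade 2 or higher related AEs are counted.

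The section's stated purpose is that "the following analyses will be conducted to compare and estimate the relative acceptability/tolerance, adherence and safety between the three study products".

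On what becomes a count, Protocol 8.3.1 allows a sign, a symptom or a disease each to be an AE. Sites document "all AEs reported by or observed in enrolled study participants regardless of severity and presumed relationship to study product". Protocol 13.4.1 lists the side effects seen with rectal products in previous studies: "mild rectal fullness; incontinence or diarrhea; flatulence; mild abdominal pain; anal discharge and proctalgia".

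The primary safety table works differently. SAP 9.1 says: "Each participant will contribute once in each category (i.e., only for highest severity AE for each participant".

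**The concern.** A Poisson model with a participant intercept assumes that, given the participant, the AE count in each period has variance equal to its mean. One bad reaction or one intercurrent illness can break that assumption by producing several records at once, for example abdominal pain and diarrhea.

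The product contrast is made within the person. The intercept therefore drops out of it, while the extra within-period variation stays. That variation is in the true variance of the rate ratio but not in the model-based standard error. The comparison could then flag a product difference because AEs arrive in groups, not because their frequency differs.

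SAP 9.1 is protected, because each participant counts once per category for each product. The count model has no such protection. At stake is a rate ratio with an interval that is too narrow, and hence a misleading exploratory signal about one formulation.

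**Working it through.** **The plan's own figures.** The SAP gives no AE rate, dispersion or error rate for this model. The nearest figures are the two tables in SAP 2.5 (n = 200), and they reproduce.
- Table 3, P(at least 5) and P(at least 10): 97.4% and 54.5% at a 5% event rate (stated 97% and 55%); 37.1% and 0.7% at 2% (stated 37% and 1%).
- Table 2, titled "Exact 2-sided 95% Confidence Intervals Based on Various Rates of Acceptability or Adherence Endpoints": recomputed powers of 90.6%, 92.8% and 33.5% against 90%, 93% and 35%.

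The 5% two-sided level used below is carried over from that table. The SAP sets none for the Poisson model.

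**Inputs from the documents.** 210 enrolled, about 200 evaluable, three periods per participant.

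**Assumed inputs.** The number of AEs per episode (K), the episode rate and the spread between participants.

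**Formula.**
1. With all three periods observed and product as the only fixed effect, conditioning on each participant's total removes the intercept. The log rate ratio is log(Tj/Tk), where Tj and Tk are the total AE counts on the two products. Its model-based SE is √(1/Tj + 1/Tk).
2. If episodes are Poisson and each gives K AEs, the true variance is larger by φ = E[K²]/E[K].
3. The true size of a nominal 5% pairwise test is 2 × [1 − Φ(1.96/√φ)].

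For a geometric K with mean m, E[K²] = m(2m − 1), so φ = 2m − 1. Example: if 25% of episodes give two AEs, E[K] = 1.25 and E[K²] = 0.75 + 0.25 × 4 = 1.75. Then φ = 1.40, 1.96/√1.40 = 1.66, and the size is 9.8%.

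**Results with identical true incidence for all products.** Simulation used 210 participants, 3,000 runs per setting, 0.1 or 0.3 episodes per period, and random-intercept SD 0 or 1. The ranges are over those settings.

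| Assumed AEs per episode | φ | Formula, pairwise | Simulated, pairwise | Simulated, 2-df product test |
|---|---|---|---|---|
| Always one | 1.00 | 5.0% | 4.0-4.6% | 4.7-5.4% |
| 10% give two | 1.30/1.10 = 1.18 | 7.1% | 5.7-6.9% | 7.6-8.2% |
| 25% give two | 1.75/1.25 = 1.40 | 9.8% | 8.9-9.8% | 11.6-12.6% |
| 50% give two | 2.50/1.50 = 1.67 | 12.9% | 12.5-13.6% | 16.1-18.1% |
| Geometric, mean 1.5 | 2.00 | 16.6% | 16.0-16.2% | 20.5-22.8% |
| Geometric, mean 2 | 3.00 | 25.8% | 25.5-26.0% | 36.7-36.8% |

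The pairwise error doubles at φ = 1.42, since 1.96/√1.42 = 1.645. Under the geometric form that is (1.42 + 1)/2 = 1.21 AEs per episode.

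**Full model fits.** Random-intercept Poisson models fitted by maximum likelihood agree.
- Pairwise (n = 200, 0.5 AEs per period, participant log-SD 0.8, 1,500 runs): 4.7%, 16.5% and 25.8% at geometric means of 1, 1.5 and 2.
- 2-df test, with period effects and 5% of participants missing period 3 (150 runs per setting, Monte Carlo SE 2 to 4 points): 5% with no clustering, 14% when 25% of episodes give two, and 21% and 32% at geometric means of 1.5 and 2.

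**Rare events.** With n = 200, a mean of 0.01, 0.02 or 0.05 AEs per participant-period gives only 2, 4 or 10 AEs per product. Pairwise simulations (participant log-SD 0.8, 4,000 runs, samples with a zero count treated as non-rejections) gave:
- mean 0.01: at most 2.5%, even at two AEs per episode;
- mean 0.02: 5.6% at 1.5 per episode and 8.2% at 2;
- mean 0.05: 15% and 22%.

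**With the fix.** A participant-clustered sandwich variance for the same log rate ratios gave 4.0% to 7.0% in every setting of the 210-participant simulations, which went up to a mean of three AEs per episode. The negative binomial and period-level random-effect alternatives were not simulated.

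**The case against.** The strongest objection is that little hangs on this analysis. It is labelled exploratory, no alpha or decision rule is attached, and Protocol 10.7.1 says that comparing the placebo products is not the purpose. That stands, and it sets the priority. A reader might infer that the model decides which formulation goes forward; nothing in the documents says so.

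A reader might also take this to be the only formal comparison of products on safety. It is not. The same SAP paragraph plans a logistic mixed model for the Grade 2 or higher related endpoint, and Protocol 10.7.2 plans Fisher's exact test. It is the only planned model-based comparison of AE counts.

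The model criticised is partly inferred. The sentences on the participant intercept and on intervals and p-values sit in the acceptability and adherence paragraph, and the latter concerns odds ratios. The safety paragraph neither specifies nor excludes a period-level effect. This stands too, and it is a reason to specify the model.

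Finally, the evidence for clustering is indirect. The list in Protocol 13.4.1 does not show that those effects occur together or are entered separately. Protocol 8.3.1 makes expected-range fecal urgency, bloating, flatulence and bleeding associated with rectal procedures non-reportable. Protocol 13.3 leaves AE assessment and reporting detail to the SSP Manual, which was not supplied and may merge symptoms into a diagnosis. So clustering is plausible, not shown.

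**Conclusion.** The concern holds as a conditional one. As written, the count model has no stated protection against extra-Poisson variation within a participant-period, and a participant intercept does not supply it.

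It is tempting to say that the model will declare false differences two to five times too often. The documents do not support that as a flat statement, because they give neither an AE rate nor a number of AEs per episode. For one pairwise contrast, two to five times corresponds to an assumed average of roughly 1.2 to 2 AEs per episode under the geometric form, with reasonably common AEs. There is no inflation at one AE per episode and less than a doubling if only 10% of episodes give two. The excess is small or absent if the count covers only events at about 0.01 to 0.02 per participant-period. That is why it matters which AEs are counted.

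The primary safety analysis in SAP 9.1 is unaffected. Priority: low to moderate.

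**What to change.** In SAP section 10, keep the Poisson mixed model for the rate ratios and add wording such as:

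> *Confidence intervals and p-values for the AE rate ratios will use a participant-clustered sandwich variance (or a participant-level bootstrap), to allow for clustering of AEs within participants and within periods. The count will include [all AEs / Grade 2 or higher related AEs only].*

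An alternative is to allow overdispersion in the model itself, through a negative binomial mixed model or a participant-by-period random effect. The safety paragraph should also state its random-effect structure directly.

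The cost is a sentence or two and a software option, with no new data.
- Intervals widen by about √φ on the log scale when AEs cluster: √1.40 = 1.18 if a quarter of episodes give two AEs, √2 = 1.41 at a geometric mean of 1.5. They barely change when AEs do not cluster.
- Sandwich standard errors are mildly anti-conservative when few participants have AEs.
- If GEE replaces the mixed model, a stronger missing-data assumption is needed. This deserves thought, because SAP 3.2 excludes participant-periods in which the product was not received and notes that COVID-19 changed how product was supplied.
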